7SH participants will return their tracking diary to the research assistant during the data collection appointment at 3, 6 and 12-months. Participants will receive a follow-up phone call monthly for the first 3 months, as this is the average time it takes to acquire a new habit. They will then receive a phone call once every 3 months till the end of the intervention period.

Outcome measures:

Primary: (measured at 12-months from intervention commencement)

- Weight change (kg, %) - between group differences

Secondary: (measured at 3, 6, 12 and 24-months from intervention commencement)

- Weight change (kg, %)
- Body Mass Index (BMI)
- Waist circumference (cm)
- Blood pressure
- Health related quality of life, using SF12
- Habit strength
- Self-Regulation of Eating Behaviour
- Fruit and vegetable intake
- Hours of physical activity performed per week
- Temperament
- Number of coach sessions attended (Sum Sanos)
- Number of habits achieved on average per week (7SH-B and 7SH-A)

Other:

Longer time frames for collecting secondary outcome measures (3, 4, 5 years) are dependent on funding.

Participant timeline: See Table 1

-t₁: Eligibility screening over the phone. Study information pack and consent form sent to participant via email. Participant makes appointment time to meet with research assistant.

t₀: Baseline appointment with research assistant. Provide written informed consent and baseline measurements.

t₁: During the baseline appointment, the participant is randomly allocated to an intervention by a member of the research team and informed of their intervention allocation. 7SH participants are given instructions on how to use the booklet or app. Sum Sanos participants are contacted within 24 hours by their assigned Health Coach. Commence intervention.

t₂: 3-month data collection.

t₃: 6-month data collection.

t₄: 12-month data collection. Participants cease intervention. Qualitative interviews.

t₅: 24-month follow-up data collection.

Table 1. Participant timeline

		STUDY PERIOD						
		Enrolment	Allocation	Post-allocation				Follow-up
TIMEPOINT		-t ₁ Screening	t ₀ Baseline	t ₁ Commence intervention	t ₂ 3 months	t ₃ 6 months	t ₄ 12 months	t ₅ 24-months
ENROLMENT	Eligibility screen	x						
	Informed consent		x					
	Allocation		x					
INTERVENTION	Sum Sanos™			←	→	→	→	
	Seven Savvy Habits Booklet			←	→	→	→	
	Seven Savvy Habits App			←	→	→	→	
DATA	Data collection/outcome measurements		x		x	x	x	x

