	Qualitative interviews						x	

Sample size: We aim to observe a difference between Sum Sanos and 7SH intervention groups at 12-months from baseline. Sample size calculations were based on mean weight loss and standard deviation from previous trials using a similar intervention to 7SH. Our power calculation suggests 35 participants are required in each of the 3 arms to achieve a 90% power and 5% significance criterion to detect a 4kg (SD 5.03) difference between Sum Sanos and 7SH intervention groups at 12 months. To account for 30% attrition, we will recruit 138 participants.

Recruitment: The research investigators will recruit participants through local public relations, including newspaper, television and radio advertisement and through social media. Our study timeline has allowed 3 months to recruit the required sample size. The recruitment progress will be monitored on a weekly basis. If the number of enrolled participants is not reaching key milestones, additional public relation outputs will be instigated.

Methods: assignment of interventions

Allocation: Computer generation randomisation will occur after baseline assessment to allocate participants to either Sum Sanos, 7SH-B or 7SH-A (allocation ratio 1:1:1). After a 1-week run-in period, participants will be informed of their study group allocation via telephone by the primary investigator. We will use minimization stratified on, BMI categories (overweight, obese class I, II, III), age (18-30, 31-43, 44-56, 57-65 years); and gender.

Implementation: Individuals interested in participating in the trial will email through their expression of interest using the contact details specified in the media advertisements. The primary investigator will speak with each individual over the phone to conduct initial screening against the eligibility criteria. If eligible, individuals will meet with the research assistant at the relevant university, to provide written consent and baseline measurements. Ineligible individuals will be recommended to see their local health care provider for weight management support.

One week after recruitment to the trial, the primary investigator will randomise participants into one of the three study arms using the clinical trial management software package, MASCoT (<https://mascot.org.au>). Participants will be informed of their allocation via telephone call from the primary investigator.

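### The protocol gives three randomisation sequences that cannot all be followed, which puts assessor blinding at risk and leaves the intention-to-treat set and time zero unfixed

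*Protocol*

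**What the plan says.** The protocol describes randomisation in three places.

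- **Participant timeline (t₁).** "During the baseline appointment, the participant is randomly allocated to an intervention by a member of the research team". The participant is told the arm there and then. "7SH participants are given instructions on how to use the booklet or app", and "Sum Sanos participants are contacted within 24 hours by their assigned Health Coach". The intervention then commences. Table 1 marks allocation in the baseline column.
- **Allocation.** "Computer generation randomisation will occur after baseline assessment to allocate participants to either Sum Sanos, 7SH-B or 7SH-A (allocation ratio 1:1:1"; and then "After a 1-week run-in period, participants will be informed of their study group allocation via telephone by the primary investigator".
- **Implementation.** "One week after recruitment to the trial, the primary investigator will randomise participants into one of the three study arms", using MASCoT, after which "Participants will be informed of their allocation via telephone call from the primary investigator".

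Four other parts of the protocol bear on the choice between them.

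- **Blinding** names the research assistants as the outcome assessors and requires them to be blinded. **Declarations of interests** relies on blinded research assistants who have no part in group allocation.
- The **opening description of Seven Savvy Habits** has research assistants give out the 7SH booklet or app. **Adherence** has 7SH participants hand their tracking diaries to the research assistant at the 3-, 6- and 12-month visits.
- **Outcome measures** times the main endpoint as "Primary: (measured at 12-months from intervention commencement", while **Sample size** speaks of 12 months from baseline.
- **Handling missing data** promises an intention-to-treat analysis with multiple imputation.

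**The concern.** Staff cannot randomise and inform a participant at the baseline visit and also do so a week later by telephone. Whoever runs the trial must choose, and the choice has three consequences.

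1. **Blinding.** If the arm is allocated, disclosed and explained at an appointment that the research assistant conducts, the person who will weigh the participant at 12 months may learn the arm on day one. Participants are not blinded, so the assessor is the main protection for the measured outcomes. The protocol also offers blinded assessment as its answer to a declared interest: a person involved in the trial co-created one intervention and developed the other.
2. **Who is randomised.** A person who withdraws in the week after the baseline visit belongs to the intention-to-treat set if already randomised, and does not exist for the analysis if not.
3. **Time zero.** Baseline, randomisation and start of intervention coincide in one sequence and not in the others, and the 12-month endpoint is tied to two different origins.

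**Working it through.** The point rests on comparing passages, not on a computed figure. The three sequences side by side:

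| | A: Participant timeline, Table 1 | B: Allocation | C: Implementation |
|---|---|---|---|
| Randomised when | During the baseline appointment | After baseline assessment, no delay stated | One week after recruitment |
| Randomised by | A research team member, unspecified | Not stated (computer-generated) | Primary investigator, MASCoT |
| Told when | Same appointment | After the one-week run-in | After randomisation, so about day 7 |
| Told how | In person | Telephone, primary investigator | Telephone, primary investigator |
| Person lost in days 1–7 | In the intention-to-treat set | In the set, if randomised before the run-in | Never randomised |
| Baseline to start | Same day; coach contact within 24 hours | About 7 days | About 7 days |

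**Can they be reconciled?** On who randomises, perhaps: the unspecified team member in A could be the primary investigator. On timing and mode of disclosure, no: same visit and in person (A) against a week later and by telephone (B and C). B and C also differ as worded, because B puts only disclosure after the run-in and C puts randomisation there.

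**Blinding.** The research assistant takes consent and baseline measurements at the appointment where A allocates, discloses and instructs. The research assistant is also the outcome assessor. A therefore puts blinding at risk; telephone disclosure by the unblinded primary investigator (B or C) avoids that step. Timing alone does not settle it. Handing out 7SH materials, and taking back 7SH diaries at 3, 6 and 12 months, would each show the research assistant that the participant is in a 7SH arm, because Sum Sanos participants show their diaries to their coaches.

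**Randomised population.** The protocol states no run-in loss, so a range has to be assumed. With 0% to 10% lost in that week, C randomises between 138 and 138 × 0.90 = 124.2, about 124. Under A all 138 are randomised, and likewise under B if randomisation precedes the run-in. The protocol does not say whether 138 counts people consented or people randomised.

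**Time zero.** The gap between baseline and start is 0 days (A) or about 7 days (B, C): 7 / 365 = 1.9% of the 12-month window, the same in every arm.

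**The case against.** Much can be said for a mild reading.

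- *B and C may be one procedure.* Randomisation after baseline assessment, with no delay stated, is literally true of randomisation a week later. On that reading two sequences remain instead of three. This is fair, but A still contradicts both, and B as worded leaves the order of randomisation and run-in open.
- *The assessor is not shown to be unblinded.* The timeline does not say that the research assistant allocates, and Declarations of interests keeps research assistants out of allocation. This stands: blinding is at risk, not demonstrably lost. The protocol does, however, place disclosure at the research assistant's visit and gives research assistants the 7SH materials and diaries.
- *Visit timing is a wording point.* Commencement appears as a scheduled timepoint, and visit windows are often left to the SAP. This largely stands for the size of the effect. The double anchor still needs correcting.

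Two stronger inferences are tempting, and the documents do not support them.

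- *That Sum Sanos follow-up drifts week by week while a coach is assigned.* Implementation sends these participants to the parent company for assignment of a coach, but the Participant timeline states coach contact within 24 hours. On that text the arms start about a day apart.
- *That run-in loss explains a fall in power below 90%.* With no run-in loss, 138 × 0.70 / 3 = 32.2 per arm, and a two-sided 5% t-test for 4 kg with SD 5.03 (4 / 5.03 = 0.795 SD) already has power 0.881. An assumed 5% loss gives 138 × 0.95 × 0.70 / 3 = 30.6 per arm and 0.864; 7% gives 29.9 and 0.856. The run-in would thus account for 1.7 to 2.5 points. The rest comes from how 138 was derived, which is a separate matter. The loss rate is also invented, and since 138 is a recruitment figure, the planned 30% attrition may already cover that week.

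**Conclusion.** The contradiction is real and sits in the operative text. The Participant timeline and Table 1 cannot be followed together with Allocation and Implementation, and those two paragraphs do not clearly agree with each other. Because this concerns trial conduct, a SAP cannot settle it.

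The main consequence is the risk to assessor blinding, which the protocol offers as its safeguard against a declared interest. The second is that membership of the intention-to-treat set depends on which paragraph is followed. How many people that affects is unknown: none if nobody leaves in the run-in week, about 14 of 138 (138 − 124) if 10% do, which is an assumption. The third, time zero, is minor: about 2% of follow-up, shared by all arms. No conclusion about loss of power or arm-dependent follow-up is drawn.

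**What to change.** Keep one sequence and correct the Participant timeline, Table 1, Allocation and Implementation to match. One that is compatible with Blinding and Declarations of interests is:

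1. The research assistant completes and saves the baseline measures.
2. The primary investigator randomises centrally in MASCoT. State whether the run-in week is kept and whether it falls before or after this step.
3. Disclosure, 7SH materials and instruction, and later collection of 7SH diaries, are handled by someone who takes no outcome measurements. The opening description of Seven Savvy Habits and the Adherence section need the same correction.
4. The randomisation date is time zero for the 3-, 6-, 12- and 24-month visits in all arms, replacing the two anchors in Outcome measures and Sample size.
5. 138 is stated to be the number randomised.

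The cost is protocol wording, one edit to Table 1, and a staff member other than the assessor for the 7SH handover and diaries. If the run-in is kept before randomisation, there is a small downside: a short gap between baseline weight and randomisation.

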Statistical methods: Analysis of covariance (ANCOVA) will be used for analysis of pre-post continuous measures collected during the study. For the primary outcome of change in weight at 12 months we will use linear regression to compare change in weight from baseline to 12 months with adjustment for baseline weight. We will use a type 3 analysis of effects to test the null hypothesis of no difference between the 3 treatment groups. If there is evidence of a difference ($P < 0.05$), further pairwise comparisons between groups will be undertaken. Similar analyses will be undertaken for other continuous pre-post outcomes. Treatment effects will be reported as mean differences with 95% confidence intervals.

We plan to finalise and publish a detailed statistical analysis plan (SAP) prior to completion of data collection and before any statistical analysis is undertaken.

Additional analyses: In addition to the primary analysis outlined above we will conduct an adjusted analysis of the primary outcome to assess the impact of any potential baseline imbalances between treatment groups that may have occurred by chance. Variables to be included as covariates for this analysis include treatment site (included as indicator variables), gender and age. BMI will not be included as it is highly correlated with baseline weight which is already included in the ANCOVA regression model.

Handling missing data: We will conduct intention-to-treat analysis. To account for missing primary outcome data, we will implement multiple imputation. In an additional analysis of the primary outcome we will use a per-protocol strategy to compare treatment groups after excluding participants who did not follow the study protocol.

Methods: Monitoring

Harms: Although we do not anticipate harms in this trial, participants are provided with the contact details of the primary investigator prior to recruitment and encouraged to make contact if they experience any harms, discomforts or adverse events. Participants may also discuss harms with the research assistant during data collection appointments. They may also speak with the primary investigator (7SH groups) or health coach (Sum Sanos) during the follow-up calls. An open-ended discussion on consequential events will be discussed during the 12-month interviews.

Ethics and dissemination

Research ethics approval: Ethics approval will be sought from the Bond University Human Research Ethics Committee in Australia.

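### The recruitment target of 138 multiplies by 1.3 instead of dividing by 0.7, so 30% attrition leaves about 32 per arm rather than the 35 required, and about 88% power rather than 90%

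*Protocol*

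**What the plan says.** All the figures stand together in the Protocol's Sample size section. The requirement is: "Our power calculation suggests 35 participants are required in each of the 3 arms to achieve a 90% power and 5% significance criterion" and the target effect is given as "to detect a 4kg (SD 5.03) difference between Sum Sanos and 7SH intervention groups at 12 months". The next sentence turns this into a recruitment target: "To account for 30% attrition, we will recruit 138 participants".

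The Allocation section sets "allocation ratio 1:1:1", so 138 means 46 per arm. The Protocol gives no other attrition rate and no other method of inflation.

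Two statements elsewhere bear on the point. Statistical methods plans a regression adjusted for baseline weight that starts with a three-group test: "We will use a type 3 analysis of effects to test the null hypothesis of no difference between the 3 treatment groups". Handling missing data adds: "To account for missing primary outcome data, we will implement multiple imputation".

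**The concern.** The requirement, the loss rate and the recruited total stand in consecutive sentences, and simple arithmetic shows that they disagree: 138 × 0.70 = 96.6, which is not 105. The pattern is that of a common slip, adding 30% to the number needed when 30% will be lost from the number recruited.

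If so, the recruitment target falls short of the trial's own requirement under the trial's own planning assumption. The power claimed for the primary comparison is then not the power that the design delivers.

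**Working it through.** **Inputs** (Sample size and Allocation sections): difference 4 kg; SD 5.03; power 90%; significance 5%; 35 required per arm; 3 arms at 1:1:1; attrition 30%; 138 recruited. The Protocol does not say whether the test is one- or two-sided. Two-sided is assumed because it reproduces the stated 35; a one-sided test would need 28.

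**Step 1. Reproduce the 35 per arm.** The standardised difference is 4 / 5.03 = 0.795.

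- Normal approximation: n = 2 × (1.960 + 1.282)² × (5.03 / 4)² = 33.2, so 34.
- Two-sample t-test: n = 34.2, so 35, with power 90.6% at 35.

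The stated 35 is therefore right for a single comparison of two arms, and the error lies in the attrition step alone.

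**Step 2. Inflate for attrition.** If a fraction d of those recruited is lost, the number to recruit is n / (1 − d).

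- Correct form: 35 / (1 − 0.30) = 50 per arm; 50 × 3 = 150.
- Multiplied form: 35 × (1 + 0.30) = 45.5, rounded up to 46 per arm; 46 × 3 = 138. This matches the stated figure exactly.
- Starting from the smaller 34 per arm, the correct form gives 34 / 0.70 = 48.6, so 49 per arm and 147 in total. Rounding therefore does not explain 138.

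**Step 3. What 138 leaves.** 46 × 0.70 = 32.2 per arm (138 × 0.70 = 96.6 in total). The shortfall is (35 − 32.2) / 35 = 8%.

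**Step 4. Power with what is left** (4 kg, SD 5.03, two-sided 5%, two arms):

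| Completers per arm | t-test | Normal approximation |
|---|---|---|
| 32 | 87.9% | 88.9% |
| 32.2 | 88.1% | 89.1% |
| 34 | 89.8% | 90.6% |
| 35 | 90.6% | 91.4% |

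At 32 per arm, the difference detectable with 90% power by the t-test is 4.14 kg rather than 4 kg.

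**Step 5. Attrition that 138 can absorb.** 1 − 35/46 = 23.9%. Beyond that, fewer than 35 per arm remain. On a continuous scale the t-test reaches exactly 90% at 34.2 per arm, or 1 − 34.2/46 = about 25.6% attrition. In whole participants, 34 per arm falls just short and 35 is needed. Either way the limit is below the planned 30%.

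**The case against.** The arithmetic mismatch is hard to dispute. The best case on the other side is that it matters little.

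- **Size.** The loss is about two points of power by the t-test and about one by the normal approximation. The detectable difference moves by 0.14 kg. No test, error rate or estimand changes. This stands, and the finding should not be read as an underpowered trial.
- **Baseline adjustment.** The planned regression adjusts for baseline weight, which may reduce the residual variance. If baseline weight correlated with weight change at an assumed 0.1, 0.2 or 0.3, power at 32.2 per arm would be 88.4%, 89.4% or 90.9%. The Protocol gives no correlation, and its 35 does not rely on one.
- **Multiple imputation.** Table 2 schedules weight at 3 and 6 months. An imputation model using those weights could recover part of the information from people who leave after these visits. It would be too strong to say that imputation recovers nothing. But the gain is not quantified, and the Sample size section, by inflating for attrition, treats those who leave as lost.
- **The three-group test.** The first test is the overall one, and its power depends on a pattern of means that the Protocol does not state. At 32 per arm it is 90.9% if the arm means are assumed to be 4, 0 and 0 kg, but 80.7% if they are 4, 2 and 0 kg. This cuts both ways and is not the calculation behind the 35.
- **Equal loss.** The figure of 32 per arm assumes the same attrition in each arm. Contact is weekly in the coached arm and much sparser in the other two, so actual losses may differ between arms. The total of 96.6 against 105 does not depend on this.

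These points limit the consequence. None of them explains how 138 follows from 35 per arm and 30%.

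**Conclusion.** The recruitment figure is wrong as written. With 30% attrition, 138 leaves about 32 per arm, 8% below the stated requirement. Power for one pairwise comparison is about 88% by the t-test that reproduces the 35 (about 89% by the normal approximation), not 90%. The number that matches the Protocol's own inputs is 150, which is 12 more.

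The error itself is certain, because it follows from three stated figures. Its effect on power is modest. The power figures assume a two-sided unadjusted comparison of two arms, equal attrition across arms, and no information from participants without a 12-month weight.

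**What to change.** Correct the last sentence of the Sample size section in one of two ways.

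1. **Keep 138 and restate the power.** For example: *We will randomise 138 participants (46 per arm). With 30% attrition, about 32 per arm are expected to have a 12-month weight, which gives about 88% power for an unadjusted pairwise comparison (4 kg, SD 5.03, two-sided 5%). The 35 per arm needed for 90% power is kept if attrition does not exceed about 24%.*
2. **Keep 90% power and 30% attrition and change the target to 150** (50 per arm).

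The first option costs one sentence and a slightly less favourable power statement, with no extra participants. The second costs 12 more participants. If the sponsor means baseline adjustment or imputation to cover the gap, the section should say so and give the correlation or gain assumed.

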Participants randomised to Sum Sanos, will be distributed to Life in Balance Pty Ltd (the parent company of Sum Sanos), to assign each participant with a health coach and commence the intervention. Participants randomised to the 7SH-B and 7SH-A groups, will be managed through the central research centre at Bond University.

Blinding: Outcome assessors (research assistants) and data analysts will be blinded to group allocation. Trial participants and the primary investigator will not be blinded to group allocation.

Methods: data collection, management and analysis

Data collection: An experienced research assistant blinded to treatment allocation will be trained by the primary investigator to collect data. The data collection timeline is presented in Table 2.

Table 2. Data collection timeline

	Baseline	3 months	6 months	12 months	24 months	Open-ended
Informed consent	x					
Demographic information	x					
Height	x					
Weight	x	x	x	x	x	x
Waist circumference	x	x	x	x	x	x
Blood pressure	x	x	x	x	x	x
Temperament (24 Q's)	x					
Questionnaires	x	x	x	x	x	x
- Habit-strength (32 Q's)						
- Self-regulation of eating (5 Q's)						
- Effortful Control (19 Q's)						
- Health related quality of life (12 Q's)						
- Fruit and vegetable intake (2 Q's)						
- Exercise behaviours (1 Q)						
Qualitative telephone interview				x		

Anthropometry:

Height will be measured in centimetres using a stadiometer with integrated level. As per NHMRC standard protocol for measuring height ¹; participants will be instructed to stand with feet together and flat on the ground (no footwear), with heels, shoulder blades and buttocks touching the wall. Participants will also be asked to look straight ahead; measurement will be taken as the participant takes a deep breath in and stretch to their fullest height.

Weight will be measured to the nearest 0.1kg using calibrated digital weight scales. As per the NHMRC clinical practice guidelines for the management of overweight and obesity ¹, participants will be asked to remove any outer garments, take off their shoes and empty pockets. Participants will be instructed to stand centred on the scale with weight evenly on both feet.

Body Mass Index will be calculated using body weight in kilograms (kg), divided by height in metres squared (m)².

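### The unblinded primary investigator screens applicants, runs the minimisation and announces each arm; with no random element stated and two conflicting accounts of allocation, the next arm is open to guessing

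*Protocol*

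**What the plan says.** All references are to the protocol.

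- **Allocation** (Methods: assignment of interventions). "Computer generation randomisation will occur after baseline assessment to allocate participants to either Sum Sanos, 7SH-B or 7SH-A (allocation ratio 1:1:1"). The method is then named: "We will use minimization stratified on, BMI categories (overweight, obese class I, II, III), age (18-30, 31-43, 44-56, 57-65 years); and gender". Every factor and cut-point is given. Nothing says whether the balancing arm is assigned with certainty or only with high probability.
- **Implementation.** "The primary investigator will speak with each individual over the phone to conduct initial screening against the eligibility criteria". After consent and baseline measurement by a research assistant, "One week after recruitment to the trial, the primary investigator will randomise participants into one of the three study arms", using MASCoT. Then: "Participants will be informed of their allocation via telephone call from the primary investigator".
- **Blinding.** "Trial participants and the primary investigator will not be blinded to group allocation". By contrast, "Outcome assessors (research assistants) and data analysts will be blinded to group allocation".
- **Participant timeline.** The t1 entry gives another account: allocation happens at the baseline visit, is done by an unspecified research team member, and the participant learns the arm there. Table 1 marks allocation in the baseline column.
- **Declarations of interests.** A co-creator of Sum Sanos is declared. The stated safeguards are blinded data collectors, a blinded biostatistician and a management committee independent of the product's parent company.

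**The concern.** Minimisation computes the next arm from the allocations already made and the new participant's factor levels. Without a random element, anyone who holds both can work out the next arm except at ties. Under the Implementation section one person holds both: the primary investigator announces every arm, so knows all past allocations, and operates the system in which the next participant's BMI class, age band and gender are used.

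The risk is selection bias. Some eligibility criteria need judgement, such as serious illness or ability to attend appointments, and no explicit rule fixes the order in which people due at the same time are entered. If more motivated people reached one arm more often, adjustment for baseline weight would not remove the effect, nor would the additional adjustment for site, gender and age. Blinding of assessors and analysts begins after assignment and does not act on this. The hypothesis favours Sum Sanos and an interest in that product is declared, so allocation should be visibly beyond influence. Nothing here suggests that anyone would steer it; the described arrangement simply cannot show that steering was impossible.

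**Working it through.** **The plan's own figures.** The protocol gives no figure for predictability. Its sample-size inputs set the scale: a difference of 4 kg, SD 5.03, 90% power and 5% significance. A two-sided two-sample t-test needs 34.2, so 35 per arm, as stated.

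**Inputs from the protocol.** 138 participants; three arms at 1:1:1; BMI in 4 classes, age in 4 bands, gender (taken as 2 levels); recruitment over 3 months.

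**Assumptions.** Equal factor weights; marginal totals; ties broken at random; factor shares of BMI 25/35/25/15%, age 15/30/35/20% and gender 70/30%, repeated with equal shares for the case random only at ties. The guesser knows all past allocations and the next participant's exact factor levels.

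**Method.** For each arm, add the new participant provisionally and sum the imbalance over the three factors. The favoured arm has the smallest sum. Three imbalance measures were used (sum of counts, range, variance), with 100 runs per setting. If the favoured arm is given with probability p, then

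P(correct guess) = p × P(one favoured arm) + (p/2) × P(two tied) + (1/3) × P(three tied).

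**Results, first set of factor shares**

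| Measure | p | One favoured arm | Two tied | Guessed |
|---|---|---|---|---|
| Sum | 1 | 0.672 | 0.262 | 0.829 |
| Range | 1 | 0.736 | 0.223 | 0.861 |
| Variance | 1 | 0.675 | 0.260 | 0.829 |
| Range | 0.8 | 0.769 | 0.198 | 0.708 |
| Sum | 0.7 | 0.775 | 0.191 | 0.621 |

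Formula check, range measure, p = 1: 0.736 + 0.223/2 + 0.041/3 = 0.861. Sum measure, p = 0.7: 0.7 × 0.775 + 0.35 × 0.191 + 0.034/3 = 0.621.

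Equal factor shares at p = 1 gave 0.826-0.863. Over all settings, including a separate run of the simulation, chance only at ties gives 67-74% determined and 83-86% guessed, and p = 0.7-0.8 gives 61-71% guessed. Simple randomisation gives 33%.

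**Entry order.** Each person is to be randomised one week after their own recruitment. 138 over about 65 working days is 138/65 = 2.1 a day, so about 2-3 people might be due together. The worst case is that the order within such a group is fully exploited, chance enters only at ties, and an unmeasured prognostic trait is fully known. The mean trait difference between Sum Sanos and the other arms is then:

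- strict order: about 0 SD
- groups of 2: about 0.15 SD
- groups of 3: about 0.27 SD

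False difference in kg = shift × correlation of the trait with 12-month weight change × 5.03. With assumed correlations of 0.1-0.3:

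- low end: 0.15 × 0.1 × 5.03 = 0.08 kg
- high end: 0.27 × 0.3 × 5.03 = 0.41 kg

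That is roughly 0.1-0.4 kg, up to about a tenth of the 4 kg target.

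**The two accounts side by side**

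| | Participant timeline | Implementation |
|---|---|---|
| Who allocates | an unspecified research team member | the primary investigator |
| When | at the baseline visit | one week after recruitment |
| How told | at the visit | by telephone |

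Both cannot be followed.

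**The case against.** **The protocol does not say the minimisation is deterministic.** This stands. The process is called computer-generated randomisation, it runs in dedicated software, and the assignment probability may sit in the system settings or be withheld from investigators on purpose. A reader might infer that there is no random element; the text supports only that none is stated. The 83-86% figure is therefore conditional. With a random element of 0.7-0.8, however, 61-71% remains guessable to someone holding the tallies, so the combination of roles matters on either reading.

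**The room to act on a guess is small.** Largely right. BMI is measured at the baseline visit, after the phone screen, and others may be allocated in between, so prediction at screening is weaker than the simulated figures. Consent and baseline measurement are complete before allocation. A reader might also assume that a whole week's intake, 138/13 or about 11 people, could be reordered at will. That would give about 0.79 SD, but the one-week rule ties each person to their own date, so the documents do not support that reading.

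**The allocator may be someone else.** The timeline allows this and would remove the week's wait. It does not settle the matter, because the Implementation section says otherwise.

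**The declared interest.** A reader might infer that the declared co-creator is the person who allocates. The available text does not identify them as the same person, and the independent committee is a real safeguard on design, though no described duty of it covers individual allocations.

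**This is detail for another document.** The exact probability can be. Who allocates, when and in what order is fixed in this protocol, and fixed inconsistently.

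**Conclusion.** The point holds in limited form. As the Implementation section stands, one unblinded person screens, allocates and announces, and can hold what is needed to guess the next arm: for 83-86% of participants if chance enters only at ties, and for 61-71% with a random element of 0.7-0.8, against 33% by chance. These figures assume exact factor levels and current tallies at the moment of allocation, and they changed little with the imbalance measure or, for the case random only at ties, with the assumed factor shares. The bias that entry order alone could produce is small, roughly 0.1-0.4 kg in a worst case that rests on assumed correlations and full exploitation. Bias through screening judgement cannot be sized from the document. Separately, and without any assumption, the participant timeline and the Implementation section contradict each other on who allocates and when. The change is worth making because it is cheap and because no later analysis can restore concealment.

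**What to change.** 1. Reconcile the participant timeline and Table 1 with the Allocation and Implementation paragraphs, so that one allocator, one time point and one way of informing participants are stated throughout.
2. In Implementation, have allocation triggered in MASCoT by an existing team member who does not screen applicants, for example the study manager mentioned under Confidentiality. Allow it only after eligibility and baseline data are locked, and strictly in order of completed baseline date. The primary investigator would learn each arm only when the participant is to be told.
3. In Allocation, state that the minimisation includes a random element, for example a probability of 0.7-0.8 for the favoured arm. The exact value can be kept in a restricted document.

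The second item matters most, since a random element alone leaves 61-71% guessable to someone with the tallies. The cost is a short amendment, a change of role within the team and slightly looser balance on the three factors. No extra staff or participants are needed.
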